5.2 Planned Duration of the Study

5.2.1 The initial imaging studies will be performed within 8 weeks of registration on the protocol, Subsequent follow up imaging will be performed within 4-6 months after registration to the study.

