9.0 Study Calendar

Table 1 Schedule of Events (time scale in weeks)

[figure not shown]
	Week						
	Pre-Study *	1-8	1-8	1-12	16-24	28-36	40-52
Informed consent	X						
Demographics	X						
Medical history	X						
Physical exam	X				X	X	X
Performance Status	X				X	X	X
CBC w/diff, plts	X				X	X	X
Serum chemistry ^a	X				X	X	X
PSA	X				X	X	X
Testosterone	X				X	X	X
Radiologic evaluation (bone scan, CT chest abd / pelvis ^b)		X			X ^f		
Targeted (Xrays) ^c		X			X ^f		
WB/axial MRI, F-18 NaF PET/CT ^d			X		X ^f		
Biopsy of suspected abnormality ^e				X			

* Prestudy tests should be performed within 8 weeks of registration.

- a) Albumin, alkaline phosphatase, total bilirubin, bicarbonate, BUN, calcium, chloride, creatinine, glucose, potassium, total protein, SGOT[AST], SGPT[ALT], sodium.
- b) If bone scan and/or CT scan and/or targeted X-rays were already performed before study registration they can be utilized for the study purposes under late registration provision, provided that patients can be registered and complete WB/axial MRI and F-18 NaF PET/CT within 8 weeks of the oldest standard study.
- c) If recommended by radiologist due to inconclusive findings on bone scan and CT scans.
- d) WB/axial MRI F-18 NaF PET/CT will be performed AFTER bone scan, CT scan and (if needed) targeted X-rays have been completed. All the imaging studies should be completed within 8 weeks of registration (except under late registration provision – see b).
- e) In patients in whom the results of WB/axial MRI and /or F-18 NaF PET/CT are consistent with recurrence or indeterminate.
- f) In patients in whom the results of all the imaging studies and biopsy (if performed) were not conclusive for metastasis. The specifics of which imaging study (or studies) to be performed at week 16- 24 will be determined based on the recommendation of radiologist.

10. Endpoint Evaluation Criteria/Measurement of Effect

All scans will be interpreted by two board-certified radiologists with CT, MRI and nuclear medicine expertise who will be dedicated members of the research team. In cases of differences in interpretation between the two radiologists, the final reading will be determined by consensus conference involving a third radiologist, also a dedicated member of the research team. One of the three possible outcomes will be assigned to the combination of CT scan and BS (and TXR) if obtained: 1) consistent with visible recurrence 2) indeterminate or 3) negative.

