10.2 Follow-up scans

Evolution of lesions over the period of time provides invaluable help in the verification of original interpretation of the scans even in the absence of biopsy. Therefore all the patients will undergo follow up scans (the type advised by radiologist) 4-6 months after registration to the protocol. These scans will be interpreted in the context of ongoing therapy (i.e. hormonal therapy) or observation. Several possible scenarios will allow us to interpret and verify the findings on the original scans.

- a) The persistence, growth, increase in numbers and intensity of enhancement of lesions in patients on observation would strongly favor the interpretation of a true positive finding.
- b) Complete stability over time or resolution of lesions without ongoing therapy would strongly favor false positive interpretation.
- c) Evolution of lesions (regression, radiologic signs of healing in the context of ongoing hormonal therapy (and lack of any history of trauma) would strongly support the interpretation of true positive scans
- d) Complete stability of lesions despite ongoing hormonal therapy would favor false positive interpretation

By combining these three elements of verification of original interpretation of WB/axial MRI and F-18 NaF PET/CT we will be able to provide the most robust assessment of sensitivity and specificity of these imaging modalities in the literature that may prove to be quite useful in the management of patients with biochemically recurrent prostate cancer.

Table 1

Interpretation of Imaging with WB/axial MRI and F-18 NaF PET/CT based on subsequent biopsy, therapy and follow up imaging (not all patients will be classified as below depending on additional systemic therapy given)

Original MRI/PET Interpretation	Biopsy	PSA response to salvage RT	Follow up scans	FINAL Interpretation of Baseline MRI/PET	
Mets	+	NA	Regardless	TP	
			Mets	Indeterminate	
			Indeterminate	FP	
			No mets	FP	
		≥ 0.04	Mets	TP	
	- or NA		Indeterminate	TP	
			No mets	Indeterminate	
	NA	Mets	TP		
		Indeterminate	TP		
		No mets	FP		
Indeterminate	+	NA	Regardless	TP	
			Mets	Indeterminate	
			Indeterminate	FP	
		≥ 0.04	No mets	FP	
			Mets	TP	
	- or NA	≥ 0.04	Indeterminate	TP	
			No mets	Indeterminate	
		NA	Mets	TP	
			Indeterminate	Indeterminate	
			No mets	FP	
Negative	N/A	<0.04	Mets	Indeterminate	
			Indeterminate	TN	
			No mets	TN	
		≥ 0.04	Mets	FN	
			Indeterminate	FN	
			No mets	Indeterminate	
		NA	Mets	Indeterminate	
			Indeterminate	TN	

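### The verification scan is timed from registration, not from the MRI/PET it verifies, so the scan-to-scan interval may be anything from about 8 to 23 weeks and the scoring rules take no account of it

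*Combined protocol and SAP*

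**What the plan says.** Section 5.2 sets both windows from the same starting point. For baseline: "The initial imaging studies will be performed within 8 weeks of registration on the protocol". For verification: "Subsequent follow up imaging will be performed within 4-6 months after registration to the study". Section 10.2 (Follow-up scans) repeats the registration anchor: "follow up scans (the type advised by radiologist) 4-6 months after registration to the protocol".

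The calendar in Section 9.0 has the MRI and PET/CT in a weeks 1-8 column, after the standard scans. Footnote d adds: "All the imaging studies should be completed within 8 weeks of registration". Footnote f gives the rescan in weeks: "The specifics of which imaging study (or studies) to be performed at week 16- 24 will be determined". The synopsis gives 4-6 months but does not say from when. Section 2.2 describes 4 weeks as the ideal period for all imaging and 8 weeks as the allowance. No section sets a minimum time between the MRI/PET and the scan that verifies it.

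Section 10.2 then interprets change over that interval. Rule (b), for patients off therapy, reads: "Complete stability over time or resolution of lesions without ongoing therapy would strongly favor false positive interpretation". Rule (d) treats stability on hormonal therapy in the same direction, and rule (a) counts persistence or growth under observation towards a true positive. The table that follows assigns TP, FP, TN, FN or Indeterminate from the baseline reading, biopsy, PSA response to salvage radiotherapy and the follow-up reading. Section 12.0 says the follow-up scans will enter the final determination of success.

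**The concern.** When a lesion is verified by its evolution, the time allowed for it to evolve is part of the test. Here that time is what remains after the delay from registration to MRI/PET is taken out of a window fixed at registration. Two patients with the same disease can be rescanned after very different intervals, both within the calendar, and be classified by the same rules.

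This matters because the follow-up reading carries real weight. Section 10.1.1 expects biopsy in only about 25% of suspicious lesions and expects the lesions to be small. Most cases will therefore be settled by PSA response, the rescan, or both. In the table, a baseline reading of metastasis with no positive biopsy and no PSA result is decided by the rescan alone. For comparison, the two verification studies described in Section 2.1 (axial MRI, and F-18 NaF PET/CT) used follow-up of 6 months and at least 6 months.

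**Working it through.** The protocol states no MRI/PET-to-rescan interval, so there is no planned figure to reproduce. The permitted interval follows from the windows.

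**Inputs**
- MRI/PET: weeks 1-8 after registration (Section 9.0); Section 5.2 says within 8 weeks.
- Rescan: weeks 16-24 (Section 9.0); 4-6 months after registration (Sections 5.2 and 10.2).
- Conversion: 365.25 / 12 / 7 = 4.348 weeks per month, so 4 months = 17.4 weeks and 6 months = 26.1 weeks.

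**Formulas**
- Shortest interval = earliest rescan - latest MRI/PET.
- Longest interval = latest rescan - earliest MRI/PET.

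| Reading | Shortest (weeks) | Longest (weeks) | Ratio |
|---|---|---|---|
| Calendar, MRI/PET weeks 1-8 | 16 - 8 = 8 | 24 - 1 = 23 | 2.9 |
| Calendar, MRI/PET weeks 0-8 | 16 - 8 = 8 | 24 - 0 = 24 | 3.0 |
| Literal months, MRI/PET weeks 1-8 | 17.4 - 8 = 9.4 | 26.1 - 1 = 25.1 | 2.7 |
| Literal months, MRI/PET weeks 0-8 | 17.4 - 8 = 9.4 | 26.1 - 0 = 26.1 | 2.8 |

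If the ideal 4 weeks of Section 2.2 is met and counted from registration, the shortest interval is 16 - 4 = 12 weeks by the calendar, or 17.4 - 4 = 13.4 by months.

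A patient imaged at week 8 reaches a literal 4-month interval at 8 + 17.4 = week 25.4, after the calendar window has closed. If 4 months means 16 weeks, he reaches it at week 24, the last permitted week.

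Late registration does not widen the range. It applies "provided that patients can be registered and complete WB/axial MRI and F-18 NaF PET/CT within 8 weeks of the oldest standard study", and registration cannot precede the oldest standard scan in that case, so MRI/PET still falls within 8 weeks of registration.

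**What a short interval does under the rules and the table in Section 10.2**
- Rules (b) and (d): an unchanged lesion favours FP. Less time makes an unchanged appearance more likely, so a slow true metastasis can be called FP.
- Rule (a): persistence under observation favours TP. The boundary with the stability rule (b) is not defined.
- Table, baseline metastasis without positive biopsy: there is no stable category. With PSA not available or at least 0.04, a rescan read as metastasis or indeterminate gives TP. A benign lesion that has not had time to resolve is therefore scored TP, where resolution would have given FP (PSA not available) or Indeterminate (PSA at least 0.04).
- Table, baseline indeterminate, PSA not available: a rescan still indeterminate stays Indeterminate; read as metastasis it becomes TP. A short interval can lose a TP here.
- Table, baseline negative: with PSA at least 0.04, a rescan showing metastasis gives FN and one showing none gives Indeterminate. With PSA below 0.04 or not available, the same two readings give Indeterminate and TN. A short interval therefore moves FN to Indeterminate, or Indeterminate to TN. Both flatter the new scans.

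**Same window counted from MRI/PET:** 16-24 weeks, ratio 24 / 16 = 1.5; in months, 17.4-26.1 weeks, also 1.5.

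**The case against.** The strongest reply is that 8 weeks is an extreme. It needs the latest permitted MRI/PET and the earliest permitted rescan, and Section 2.2 aims for imaging within 4 weeks. That stands: 8-23 weeks is what the plan allows, not what it expects, and the documents give no scheduling data. It does not remove the point, because footnote d requires MRI/PET to follow the standard scans inside the same 8 weeks, so late MRI/PET is foreseeable.

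Reach is also limited. A positive biopsy gives TP whatever the rescan shows. The criterion of at least 4 of 45 in Section 12.0 counts readings on the new scans. PSA response to salvage radiotherapy enters many rows of the table, and the lettered rules say only that a finding favours an interpretation. All of this stands. The classification and the final determination of success nevertheless still use the rescan.

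A reader might infer that late-imaged patients are systematically pushed towards FP, and late-imaged negatives towards TN. The documents do not support that as a general statement. The first follows from rules (b) and (d) taken alone; rule (a) and most rows for a persisting lesion point the other way. For negatives, scan timing never moves a patient from FN to TN within a given PSA stratum. It moves FN to Indeterminate or Indeterminate to TN.

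**Conclusion.** The concern holds as a matter of an uncontrolled verification interval, not as a bias of known direction. By the calendar the permitted interval is 8-23 weeks; by literal months it is about 9-25 weeks. It is at least about 12 weeks if the 4-week ideal is met from registration.

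The range rests only on the protocol's windows. That a lesion shows less change over 8 weeks than over 23 is a reasonable assumption, but the documents give no growth rate, so the number of patients reclassified cannot be estimated. The results exposed are the TP/FP/TN/FN classification, the sensitivity and specificity drawn from it, and the part of the final determination of success that relies on follow-up scans. This is a worthwhile and inexpensive improvement; it does not undermine the primary count.

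**What to change.** In Section 5.2, Section 9.0 (footnote f) and Section 10.2 (Follow-up scans), count the protocol's existing 4-6 months from the baseline WB/axial MRI and F-18 NaF PET/CT, taking the later of the two, instead of from registration. Give the synopsis the same anchor, align the calendar column, and reconcile weeks 16-24 with 4-6 months (17.4-26.1 weeks). Record the interval for each patient.

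The number of scans does not change. For late-imaged patients the rescan moves up to about 8 weeks later, to 8 + 26.1 = about week 34 at most, inside the 52-week follow-up of Section 5.3. The cost is that it may no longer coincide with the week 16-24 visit at which PSA is drawn, so the calendar needs more than a changed word. The retained 4-6 months also remains shorter at its lower end than the 6-month precedents in Section 2.1.

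If the registration anchor is kept, record the interval, report its distribution, and present the TP/FP/TN/FN results with a sensitivity analysis that excludes short intervals, with the cut-off fixed before the follow-up scans are read. That costs one derived variable and one extra table.

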5.3 Subject Follow-Up

Patients will be followed clinically and will undergo periodic laboratory and radiographic tests until week 52 or until disease progression requiring therapy (see Study calendar 9.0).

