Patients who were classified as having negative bone scan and CT scan (estimated $\geq 90\%$ of patients) will undergo MRI (axial MRI and WB MRI) and F-18 NaF PET/CT. The outcome of these studies will be reported as 1) consistent with visible recurrence, 2) indeterminate 3) negative. In cases of findings consistent with visible recurrence or indeterminate a biopsy of the lesion of interest will be recommended if feasible. Any enrolled patient without a positive biopsy will be followed and their treatment (at discretion of treating physician), PSA values and outcome will be recorded to evaluate the scan result specificity and sensitivity in relation to additional information provided with follow-up (e.g. if patients undergo Salvage Radiation Therapy, PSA response will be recorded which will have significant implication in the interpretation of radiologic findings (see 10). Subsequently all patients without biopsy proven metastasis will undergo follow up imaging studies (the type of imaging to be recommended by radiologist)) within 4-6 months to reassess any abnormalities in the context of time, ongoing therapy or no therapy.

Sample Size:

Total Sample size is 56. Anticipated accrual is 2-3 patients a month.

Estimated Duration of the Study

24 months

Summary of Subject Eligibility Criteria:

Patients with 2 PSA values ≥ 0.2 ng/mL at least 4 weeks after surgery will be evaluated. Patients who were started on androgen deprivation therapy will not be allowed on this protocol. Patients who have started radiographic evaluation and underwent CT scan and/ or BS prior to registration to the study will be able to participate under a late registration provision, provided that WB/axial MRI and F-18 NaF PET/CT can be completed within 4 weeks of the CT scan and BS.

Investigational Product Dosage and Administration:

Not Applicable.

Clinical Observations and Tests to be Performed:

CT of the chest, abdomen and pelvis and bone scan. Targeted X Rays if suggested by the radiologist. If negative, WB/axial MRI and F-18 Sodium Fluoride PET /CT. Biopsy of suspected lesions will be performed if feasible, and repeat scans will be performed for patients with suspicious lesions.

Statistical Considerations:

Sponsor/Licensee:

City of Hope

Case Report Forms

Table of Contents

SECTION	PAGE
1.0 Objectives	8
2.0 Background.....	9
2.1 Introduction/Rationale for Development	9
2.2 Overview of Proposed Study	11
3.0 Patient Eligibility	12
3.1 Inclusion Criteria	12

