Biopsy, when feasible recommended in all patients with MRI or NaF PET/CT consistent with recurrence or indeterminate Record PSA response to Salvage Therapy (if given), perform 4-6 month follow up scans if clinically indicated and follow for 1yr or until progression

Patients who have CT scan and /or bone scan that are consistent with or indeterminate for metastases will be managed in a standard fashion at the discretion of treated physician. It may include additional imaging studies, biopsies and subsequent therapy. Patients with CT scan and bone scan interpreted as negative (estimated $\geq 90\%$) will undergo additional imaging, including WB/axial MRI and F-18 NaF PET/CT. Possible outcomes :1) consistent with recurrence 2) indeterminate 3) negative will be assigned to WB/axial MRI and F-18 NaF PET/CT. In cases of WB/axial MRI interpreted as consistent with visible recurrence or indeterminate a biopsy of the lesion of interest will be recommended if feasible.

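### Section 5.3 and the Section 10 flow text end follow-up at progression, while the Synopsis, Section 5.2.1 and Section 10.2 (Follow-up scans) require the verification data with no such stop

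*Combined protocol and SAP*

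**What the plan says.** Two places end follow-up at progression. Section 5.3 (Subject Follow-Up) has patients undergo "periodic laboratory and radiographic tests until week 52 or until disease progression requiring therapy". The Section 10 flow text says "follow for 1yr or until progression", and just before that "perform 4-6 month follow up scans if clinically indicated". The two stops are worded differently: one needs progression that calls for therapy, the other progression alone. Neither term is defined.

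Three places set no such stop:

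- **Synopsis, on treatment, PSA and outcome:** "Any enrolled patient without a positive biopsy will be followed and their treatment" is to be recorded, and "PSA values and outcome will be recorded to evaluate the scan result specificity and sensitivity".
- **Synopsis, on imaging:** "Subsequently all patients without biopsy proven metastasis will undergo follow up imaging studies" within 4-6 months, to be reassessed with or without therapy.
- **Section 5.2.1:** follow-up imaging at 4-6 months after registration, with no exception.
- **Section 10.2 (Follow-up scans):** "Therefore all the patients will undergo follow up scans (the type advised by radiologist) 4-6 months after registration to the protocol". It adds: "These scans will be interpreted in the context of ongoing therapy (i.e. hormonal therapy) or observation". Its scenarios (c) and (d) apply only to men on hormonal therapy.

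Section 12.0 brings follow-up scans and treatment results into the final determination of success.

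**The concern.** The verification plan depends on what happens after the baseline scans. Section 10.1.1 expects biopsy in only about 25% of cases with suspicious lesions, which leaves about 100% − 25% = 75% to be judged on PSA response and follow-up imaging. Men with negative newer scans have no biopsy route in the interpretation table at all.

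A site that works from Section 5.3 could stop tests in a man who progresses early. A site that works from Section 10.2 would scan the same man and read the scan in the light of his therapy. If the first reading prevails, verification is missing for a reason plausibly connected with the fact to be verified, namely whether he had metastases at baseline. Data not collected for that reason cannot be recovered at analysis.

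**Working it through.** **1. The plan's own figure, to mark what is not at stake.** Section 12.0 requires at least 4 positives among 45 men negative on standard scans, with type I error below 5% at a 3% rate and power above 86% at 15%. The exact binomial tail is P(X ≥ 4) = 1 − Σ(k = 0 to 3) C(45,k) p^k (1−p)^(45−k). It gives 0.0456 at p = 0.03 and 0.9215 at p = 0.15, so both stated inequalities hold. The count is of positives on the baseline newer scans, so Section 5.3 does not change it.

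**2. Which tests Section 5.3 would stop.** Section 5.3 points to the Study Calendar. After baseline, the calendar lists imaging in one column only, weeks 16-24 (footnote f). PSA is listed at weeks 16-24, 28-36 and 40-52. The radiographic tests that Section 5.3 can cut short are therefore the verification scans themselves. Neither the calendar columns nor footnote f carries a progression stop.

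**3. One man under both rules.** Suppose he has no positive biopsy, progresses at month 3 (3 × 52/12 = week 13) and starts hormonal therapy.

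- Under Section 5.3 his tests end before week 16.
- Under Section 5.2.1 and the Synopsis he is imaged at 4-6 months.
- Under Section 10.2 he is imaged, and scenario (c) or (d) says how to read the result.

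If he progresses after the week 16-24 scan, Section 5.3 removes only later PSA and clinical follow-up.

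**4. What the interpretation table does without the scan.** In the legible rows of the table at the end of Section 10.2, the follow-up scan column takes four entries: metastases, indeterminate, no metastases, or regardless. The last belongs to biopsy-positive men. PSA response has a not-applicable level; the follow-up scan has none. The final category of indeterminate is assigned to specific combinations that include a scan result, not to a missing scan. The table is partly broken in the text available, so this rests on the rows that can be read.

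**5. Salvage radiation.** Section 10.2 (PSA Response To Salvage Radiation Therapy) expects most patients to be offered this treatment and uses the PSA 6-8 weeks after it ends. The documents do not say whether a rise in PSA that leads to salvage radiation is progression requiring therapy. If it were read that way, this PSA would also fall after the stop.

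**6. Direction of any bias.** Let a and b be the shares of true positives and false negatives that lose verification. Apparent sensitivity is TP(1−a) / [TP(1−a) + FN(1−b)]. It equals the true value when a = b, is too high when b > a, and too low when a > b. Biopsy protects some true positives, which argues for b > a. Men with visible lesions might progress sooner, which argues for a > b. The documents give neither rate.

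**The case against.** The strongest reply is that the plan already requires the data. The Synopsis, Section 5.2.1 and Section 10.2 all call for the scans, and the man who starts hormonal therapy is the case that scenarios (c) and (d) were written for. Section 5.3 limits tests, whereas the Synopsis separately requires PSA values, treatment and outcome to be recorded. This stands in part: the defect is a contradiction, not a settled loss of data. It does not remove the problem, because the scans that Section 5.3 would stop are the ones the other passages require.

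Second, the caption of the interpretation table admits that not all men will be classified, depending on systemic therapy. That is a fair disclosure, but it gives no handling for a missing scan. Such scans can also be missing for other reasons, such as the clinical-indication wording in the flow text, so Section 5.3 is not the only source of this gap.

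Third, sensitivity and specificity are not among the objectives in Section 1.0 or the endpoints in Section 12.0, and imaging that shows progression may itself help verification. Both points limit the reach. Even so, the Synopsis and Section 10.2 state the aim of assessing sensitivity and specificity, and Section 12.0 uses follow-up in judging success.

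A reader might go further and infer that the loss falls mainly on men with real metastases, so that apparent sensitivity is inflated. The documents do not support that. They give no rate of progression before week 16-24, overall or by scan result, and equal proportional loss of true positives and false negatives leaves sensitivity unchanged.

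**Conclusion.** The point holds as an inconsistency that should be reconciled. Section 5.3 and the Section 10 flow text end follow-up at progression; the Synopsis, Section 5.2.1 and Section 10.2 (Follow-up scans) do not. Followed literally, Section 5.3 leaves a man unclassifiable if he has no positive biopsy and progresses before his week 16-24 scan.

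What is exposed is the verification of baseline readings and the follow-up part of the final determination of success. A reader might also infer that the primary result is compromised. It is not: the baseline count of at least 4 of 45 does not depend on Section 5.3, and biopsy-positive men are true positives whatever later scans show.

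The possibility of bias rests on one assumption, that early progression is related to true metastatic status. That is plausible, but the documents neither show nor quantify it, so no direction or size is claimed.

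**What to change.** Reconcile Section 5.3 and the Section 10 flow text with the Synopsis, Section 5.2.1 and Section 10.2 (Follow-up scans):

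- State that progression, or the start of any therapy, is recorded with its date and type, but does not by itself end collection of the verification data already planned: PSA, outcome, and the week 16-24 scan where the calendar lists it.
- Define the stopping term once, use it in both places, and state whether salvage radiation counts as therapy for progression.
- Add to the interpretation table that men with no follow-up scan, and no positive biopsy, are reported as unverified, with their number and the reason.

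Treatment decisions stay with the treating physician; nothing here proposes a clinical rule.

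The cost is a wording amendment, continued data collection in men who progress or start therapy, and, for a few men, a scan that Section 5.3 alone would have skipped. Section 13.6 assigns standard scans to the participant or insurer and the newer scans to the study budget, so the payer for those few scans depends on the type the radiologist advises.
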